In addition to challenges to maternal health, patients with lupus have poor obstetric outcomes compared with women without SLE, including a greater likelihood of fetal loss (approximately 3-fold increase) and a greater incidence of preterm deliveries [~40% vs. 10% among healthy women] [Clark, 2003; Clowse, 2005]. Recently a meta-analysis addressing this subject was reported [Smyth, 2010]. The proportion of pregnancies in women with SLE resulting in fetal death has been reported to be 15%-20% in European studies [Cortes-Hernandez, 2002; Julkunen, 1993] and 15%-25% in North American

studies [Clowse, 2005; Andrade, 2008], with stillbirths accounting for 2%-4% of these outcomes.

The presence of anti-phospholipid antibodies has been reported in 30%-80% of patients with SLE [Mecacci, 2009], and is associated with an increased risk of spontaneous miscarriage and poor maternal and/or fetal outcome [Cortes-Hernandez, 2002; Clark, 2007]. In prospectively examined pregnancies, with anti-Ro and anti-La antibodies in the mother, the prevalence of congenital heart block (with mortality of approximately 20%-30%) is between 1% and 5%, and rises to between 6% and 25% when another pregnancy was affected in the same mother [Jaeggi, 2010; Friedman, 2010]. Active SLE and associated comorbidities (proteinuria, anti-phospholipid syndrome, thrombocytopenia, and hypertension) have also been noted to be important predictors of fetal loss [Clowse, 2006; Cortes-Hernandez, 2002; Julkunen, 1993].

A cohort of SLE pregnancies from a single academic medical center in the US identified risk factors for fetal loss and pre-term delivery. Among pregnant patients with high SLE disease activity (Physician Global Assessment [PGA] score ≥ 2), 42% had fetal loss during the first trimester compared to 14% among women with low activity (PGA < 2). Same pattern was observed during the second (32% vs. 7%, respectively) and third trimesters (10% vs. <1%, respectively) among pregnant patients with high SLE disease activity vs. women with low activity. The combination of high disease activity, with low complement and/or anti-ds DNA auto antibodies, during the second trimester increased the risk of fetal loss and preterm delivery pregnancy outcomes [Clowse, 2011].

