
Elective Termination
	
Defined as deliberate termination of pregnancy at any time in gestation by surgical or medical means. Reasons for elective abortions are captured and are classified as due to medical reasons or social reasons.
	
Pregnancies
	
Included counted as one case if all multiple pregnancies ended in elective termination. Pregnancy is counted as a live birth outcome if at least one pregnancy resulted in a live-born infant
	
During pregnancy
	
3 months prior to LMP and/or at any time in pregnancy³ prior to outcome
	
Cohort 1: Elective termination among all pregnancies¹ with exposure at any time in pregnancy³; Cohort 2: Elective termination among all pregnancies¹ with no exposure at any time in pregnancy³;

Preterm Delivery
	
Defined as a spontaneous or induced delivery at <37 gestational weeks, reported by the mother and validated through the medical record. Please refer to Section 8.3.1 for further description of the method for defining gestational age and therefore preterm birth.
	
Pregnancies ending in live births
	
Excluded due to inherent higher risk of preterm birth in multiple
	
At birth
	
3 months prior to LMP and/or at any time in pregnancy³ prior to 37 weeks
	
Cohort 1: Preterm delivery among pregnancies enrolled prior to 37 weeks' gestation and ending in at least one live birth, with exposure at any time in pregnancy³ prior to 37 weeks; Cohort 2: Preterm delivery among pregnancies enrolled prior to 37 weeks' gestation and ending in at least one live birth, with no exposure at any time in pregnancy³;

Outcome	General definition	Denominator	Pregnancy involving multiples	Outcome assessment	Exposure time	Endpoints
Infant Outcomes (Secondary)						

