	
minor structural defects: "hair pattern unruly", "prominent nasal bridge", and "clinodactyly 5th finger bilateral", this would constitute one specific pattern of minor structural defects. For each specific pattern identified in Cohort 1, infants in Cohorts 2 who have the same specific pattern(s) are selected to comprise the numerator for those cohorts. In infants who have more than one specific patterns of at least 3 minor structural defects, each specific pattern will qualify as its own endpoint; therefore, the infant would be counted more than once.
					
infants, with ≥ 3 minor birth defects of any type identified, with no exposure at any time in pregnancy³;

Post-natal growth deficiency
	
Defined as postnatal size at approximately 1 year of age (weight, length or head circumference) less than or equal to the 10th percentile for sex and age using National Center for Health Statistics (NCHS) pediatric growth curves, and adjusted postnatal age for premature infants if the postnatal measurement is obtained at less than 1 year of age. [CDC, 2000].
	
Live born infants
	
Excluded due to inherent higher risk of reduced birth size in multiple
	
From birth up to 1 year of age
	
3months prior to LMP and/or at any time in pregnancy³
	
Cohort 1: Post-natal growth deficiency identified up to 1 year of age among live born infants with exposure at any time in pregnancy³
 
Cohort 2: Post-natal growth deficiency identified up to 1 year of age among live born infants, with no exposure at any time in pregnancy³

Developmental concerns
	
Defined as an abnormal score within the scoring guidelines of the Ages and Stages Questionnaire (ASQ) (Squires, 2009). The ASQ is administered at 12 months of age as a screening tool for developmental milestones by parent report. The ASQ-3 will be sent electronically to the participant or, if the participant prefers, a hard copy questionnaire will be mailed for completion.
	
Live born infants
	
Included each counted separately
	
At 1 year of age
	
3months prior to LMP and/or at any time in pregnancy³
	
Cohort 1:Developmental concerns identified at 1 year of age among live born infants, with pregnancy exposure at any time in pregnancy³;
 
Cohort 2: Developmental concerns identified at 1 year of age among live born infants, with no exposure at any time in pregnancy³

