8.6.3. Timings of Assessment during follow-up

Table 5 Timing of Cohort Enrollment, Interviews, 2 Medical Records

	Any Time in Pregnancy	20-22 Weeks' Gestation	32-34 Weeks' Gestation	0-6 Weeks Post-Delivery	0-12 Months Post-Delivery	1 Year Post-Delivery
Referral	√					
Enrollment and Consent	√					
Enrollment Interview	√					
Interim Interview I		√				
Interim Interview II			√			
Pregnancy Outcome Interview and Request for Medical Records*				√		
Pregnancy Medical Record Review					√	
Pediatric 1-Year Medical Records Request and Review						√
Pediatric 1-Year ASQ						√

*Contact earlier if pregnancy outcome occurs earlier

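### Postnatal growth deficiency: age is corrected for prematurity only before the first birthday, so the same preterm infant is graded differently on either side of the planned 1-year measurement

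*Protocol*

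**What the plan says.** In Table 2 (Section 8.3.2) the definition column reads "Defined as postnatal size at approximately 1 year of age (weight, length or head circumference"), with the cut-off "less than or equal to the 10th percentile for sex and age" on national growth curves. It then calls for "adjusted postnatal age for premature infants if the postnatal measurement is obtained at less than 1 year of age". The Glossary (Section 14) repeats the same condition. No other section extends the correction to a measurement taken at or after the first birthday.

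The timing is described in several places:

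- Section 8.7.1 places the endpoint at about 1 year.
- Table 5 (Section 8.6.3) schedules "Pediatric 1-Year Medical Records Request and Review" in its column for 1 year post-delivery.
- The endpoint column of Table 2 has the looser "Post-natal growth deficiency identified up to 1 year of age among live born infants with exposure at any time in pregnancy", and the assessment column likewise runs from birth to 1 year.

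On prematurity, Section 6.1 reports "a greater incidence of preterm deliveries [~40% vs. 10% among healthy women"]. Table 2 defines preterm delivery as "Defined as a spontaneous or induced delivery at <37 gestational weeks" and analyses it as an outcome of its own. For small for gestational age, Table 2 uses separate charts for preterm infants. Multiples are left out of the growth endpoint: "Excluded due to inherent higher risk of reduced birth size in multiple".

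**The concern.** An age-specific percentile means what it should only if age is counted on the same basis for every infant. The rule changes that basis at 1 year, which is also the time the endpoint is meant to be measured. Whether a preterm infant is classed as growth-deficient can then depend on which side of the birthday a routine visit happened to fall.

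Two things make this more than cosmetic. The protocol itself expects preterm birth to be common in this disease. It also takes care over gestation-related size elsewhere, with preterm charts for small for gestational age and the exclusion of multiples here. At stake is how cleanly the endpoint separates growth after birth from early delivery, which the study already analyses separately.

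**Working it through.** The protocol gives no expected rate, power or sample size for this endpoint, so there is no stated figure to reproduce. The check has three steps.

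**1. Size of the age gap.** The gap is 40 weeks minus gestational age at birth. At 52 weeks of chronological age:

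| Born at (weeks) | Gap (weeks) | Corrected age (weeks) |
|---|---|---|
| 36 | 4 | 48 |
| 34 | 6 | 46 |
| 32 | 8 | 44 |
| 28 | 12 | 40 |

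Before the birthday the infant is graded at corrected age. From the birthday on, the same infant is graded against norms for about 52 weeks.

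**2. Effect on the rate.** Inputs:

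- 10th percentile cut-off (Table 2), z = −1.2816.
- Preterm share 40% (Section 6.1).
- Shift *s* in size-for-age from using uncorrected age. This is an **assumption**, 0.2 to 0.6 SD, because the protocol gives neither growth-curve values nor a distribution of gestational age.
- All preterm infants measured at or after 1 year. This is also an **assumption**, and an upper bound.

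For a preterm infant growing normally for corrected age, the chance of falling at or below the cut-off on one measure is P = Φ(−1.2816 + *s*):

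- *s* = 0.2: Φ(−1.0816) = 14.0%
- *s* = 0.6: Φ(−0.6816) = 24.8%

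Cohort rate = 0.6 × 10% + 0.4 × P:

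- *s* = 0.2: 6% + 5.6% = 11.6%
- *s* = 0.6: 6% + 9.9% = 15.9%

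With corrected age throughout, *s* = 0 and the rate is 10%. Taking the 170 live-birth pregnancies per cohort anticipated in Section 8.5, the excess is 170 × 0.4 × (P − 0.10), or about 3 to 10 infants per measure.

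**3. Effect on the comparison.**

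*Equal preterm rates (40% in both cohorts), true relative risk 2.0.* The exposed cohort has a correctly graded rate of 20% (z = −0.8416). Its preterm infants then have probability Φ(−0.8416 + *s*) = 26.1% at *s* = 0.2 and 40.5% at *s* = 0.6. The observed exposed rate is 0.6 × 20% + 0.4 × that probability:

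- *s* = 0.2: 22.4% / 11.6% gives 1.94
- *s* = 0.6: 28.2% / 15.9% gives 1.77

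The error pulls the estimate toward 1. With no true effect the ratio stays at 1.

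*Unequal preterm rates, no growth effect.* Take 40% versus 30%, an **assumed** contrast. The rate at 30% preterm is 0.7 × 10% + 0.3 × P:

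- *s* = 0.2: 11.2%, so 11.6 / 11.2 gives 1.04
- *s* = 0.6: 14.4%, so 15.9 / 14.4 gives 1.10

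**The case against.** The strongest reply is that the rule is explicit, is the same in both places and applies to both cohorts, and that the age at which correction for prematurity stops is a convention. Growth is abstracted from birth to 1 year (Table 3), so many last measurements may predate the birthday and be corrected. Disease severity is a listed confounder (Section 8.3.3), and propensity scores are built for each endpoint separately (Section 8.7.3).

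Part of this stands. The share of measurements taken after the birthday is unknown, so the figures are an upper bound on that point, and the SD shift is assumed. The rest does not remove the problem. A convention that switches at the planned measurement time makes grading depend on visit timing. Section 8.3.3 names previous preterm delivery, not the gestational age of the index infant, and weighting on maternal factors cannot repair an outcome graded on the wrong age.

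A reader might infer three stronger points, none of which the protocol supports:

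- *Preterm birth is simply counted as growth deficiency, so the endpoint cannot answer its question.* On the assumptions above only a further 4 to 15 in 100 preterm infants cross the cut-off per measure (14.0% or 24.8% against 10%).
- *The rule creates a false belimumab signal.* The 40% versus 10% contrast compares SLE with healthy women. Here both cohorts have SLE and the design seeks similar severity. Nothing in the protocol supports a particular preterm imbalance between them.
- *Any low reading since birth counts as a case.* The definition in the same row, the Glossary and Section 8.7.1 all fix the endpoint at about 1 year. The looser wording in the other two columns can be read as the follow-up window, so it is a minor inconsistency.

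**Conclusion.** The point holds in a limited form. As written, the rule misgrades preterm infants measured at or after 1 year, and it does so at the time the endpoint is defined. It inflates the deficiency rate in both cohorts, from 10% to at most about 11.6–15.9% per measure under the assumed 0.2–0.6 SD shift, 40% preterm and all preterm measurements at or after the birthday. With equal preterm rates and measurement timing, the main consequence is dilution: a true relative risk of 2.0 would read as about 1.94 to 1.77. A spurious ratio arises only if preterm rates or measurement timing differ between cohorts, and it is small at the assumed 40% versus 30%. The primary outcome, the sample size and the other secondary endpoints are untouched. Because the protocol states the rule twice, an analysis plan that follows it would inherit the problem.

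**What to change.** In Table 2 and in the Glossary, delete the condition that limits the correction to measurements before 1 year, and state that gestation-corrected age is used for every preterm infant at the study measurement. Align the assessment and endpoint columns of the Table 2 row with the definition at about 1 year. If comparability with earlier studies is wanted, keep the present rule as a sensitivity analysis.

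The cost is a wording change. Gestational age is already determined under Section 8.3.1 and postnatal growth is already abstracted from pediatric records, so no new data are needed. The one drawback is that the main rates become slightly less comparable with studies that used the older convention.

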8.3.3. Confounders and effect modifiers

The potential confounders/effect modifiers listed below will be considered in multivariable analyses, where possible, as well as others that are relevant to each of the study outcomes:

- Maternal and paternal age
- Previous pregnancy history: gravidity and parity, previous spontaneous abortions and elective terminations
- Maternal and paternal race/ethnicity, education, occupation, socioeconomic status
- Pre-pregnancy body mass index
- Previous preterm delivery
- Previous child with a birth defect
- Maternal conditions: e.g., depression, diabetes
- Maternal exposures: gestational timing and dose of all over-the-counter and prescription medications, including all medications for the treatment of SLE used during pregnancy; vitamin and mineral supplements, herbal products; illnesses; fever; vaccinations
- Prenatal testing: ultrasound and other prenatal tests; timing in gestation and results
- Pregnancy complications: e.g., pregnancy induced hypertension, gestational diabetes, prolonged labor (definitions included in Section 14 Glossary)
- Maternal lifestyle habits: cigarette smoking, alcohol consumption and illicit drug use
- SLE disease severity assessment (see ANNEX 1 [Section 15.1] for details)
- Relevant lab values where available (e.g., CBC with differential, urinalysis: protein, red blood cell (RBC), white blood cell (WBC), casts, urine protein:creatinine ratio, dsDNA antibody, anti-phospholipids C3 and C4)
- Infant complications: e.g., hospitalizations, congenital heart block,
- Relevant pediatric exposure: any vaccines administered, infections requiring hospitalization in first year of life, breastfeeding status

Methods for identifying and controlling for these confounders and/or effect modifiers are described in Section 8.7.1. The SAP will provide greater detail on the definitions of, the identification of and the controlling for confounders and/or effect modifiers.

8.4. Data sources

Maternal Interviews: In the two cohort study groups, as well as the case-series, data are collected by semi-structured maternal telephone interview on two to four occasions (depending on gestation age at enrollment) during and shortly after completion of pregnancy (please see [Table 3](#) and [Table 6](#) for specific timing and content of interviews).

The interviews include data on exposure timing, dose, and duration for all medications, including belimumab, taken anytime in pregnancy as well as data on a wide variety of confounders (See Section [8.3.3](#)).

For women exposed to belimumab or other medications used for the treatment of SLE, information on disease severity is obtained directly from the mother at every interview (intake/enrollment and 32 week's gestation and outcome assessment maternal telephone interviews) (see [ANNEX 1](#) [Section [15.1](#)] for information on patient disease severity assessments). At the conclusion of pregnancy, regardless of the outcome, participants are interviewed about the outcome including presence or absence of birth defects, pregnancy and infant complications and infant size.

Medical Records: Mothers are asked to release medical records to the study investigators from their obstetrician or other obstetric provider, specialty care provider such as their rheumatologist/nephrologist, hospital of delivery, pediatrician, and any other health care provider involved in the pregnancy. These records are abstracted and used to validate pregnancy and infant outcomes and when necessary to provide details regarding timing or dose of belimumab and other medications used for the treatment of SLE in the absence of complete information from maternal report as well as validating any potential confounders/effect modifiers. Pre-defined definitions for each of the study outcomes are used for classification ([Table 2](#)).

Validation of classification of major birth defects, the primary outcome, is conducted periodically and before each annual and final study reports by the Co-Investigator and dysmorphologist, who is an expert in diagnosing birth defects.

Other data sources used within the study include Ages and Stages Questionnaire (ASQ-3) self-administered by mother and the dysmorphological physical examination for infant outcomes assessments

Table 3 Variables collected per cohort

Variable	Cohort 1 Belimumab- exposed	Cohort 2 Disease comparison	Case-Series Belimumab- exposed (non- cohort)	Data Collection Time Period
Maternal Interviews⁶				
Belimumab exposure timing	√		√	At every interview
Belimumab dose	√		√	At every interview
Belimumab duration	√		√	At every interview
Pregnancy Outcomes				
Any birth defects	√	√	√	At every interview
Other pregnancy outcomes ⁴	√	√	√	At outcome interview
Infant Outcomes (up to 1 year of age)				
Infant size	√	√	√	At outcome interview
Serious infections	√	√	√	At outcome interview
Developmental concerns ⁸	√	√	√	1 year of age
Potential confounders/effect modifiers				
Maternal/paternal characteristics	√	√	√	At enrollment interview
Self-reported disease severity	√	√	√	At every interview
Previous pregnancy and delivery birth defect history	√	√	√	At enrollment interview
Maternal conditions	√	√	√	At every interview
Other maternal exposures/concomitant medications ¹	√	√	√	At every interview
Maternal lifestyle habits	√	√	√	At every interview
Prenatal testing	√	√	√	At every interview
Pregnancy complications	√	√	√	At every interview
Infant complications and pediatric exposures	√	√	√	At outcome interview
Medical Record Abstraction^{2,7}				
SLE diagnosis validation ⁵	√	√	√	Medical history
Pregnancy validation	√	√	√	Medical history
Belimumab Exposure				
Exposure timing, dose, duration validation	√		√	Preconception to pregnancy outcome
Pregnancy Outcomes				
Major birth defects ^{3,9}	√	√	√	LMP to infant 1 year of age
Other pregnancy outcome validation ⁴	√	√	√	LMP to pregnancy outcome
Infant Outcomes (up to 1 year of age)				
Birth and postnatal growth	√	√	√	Birth to 1 year of age

Variable	Cohort 1 Belimumab- exposed	Cohort 2 Disease comparison	Case-Series Belimumab- exposed (non- cohort)	Data Collection Time Period
Serious infections	√	√	√	Birth to 1 year of age
Minor birth defect patterns ^{3,9}	√	√	√	Birth to time of dysmorphology examination
Potential confounders/effect modifiers				
Clinically assessed disease severity	√	√	√	Preconception to pregnancy outcome dependent on last clinical assessment
Previous pregnancy, delivery birth defect history validation	√	√	√	Medical history
Maternal conditions validation	√	√	√	Medical history
Maternal exposure/concomitant medications ¹ validation	√	√	√	Preconception to pregnancy outcome or within 2 years of LMP for specific exposures
Prenatal testing validation	√	√	√	LMP to pregnancy outcome
Infant complications and pediatric exposures	√	√	√	Birth to 1 year of age
Infant vaccination status	√	√		Birth to 1 year of age
Birth and postnatal growth	√	√	√	Birth to 1 year of age
Serious infections up to 1 year of age	√	√	√	Birth to 1 year of age

¹ For cohorts 1 & 2 primarily medications used for the treatment of SLE will be assessed.

² Information will be dependent on the completeness of the medical record

³ Performed periodically and before each annual and final study reports

⁴ Includes preterm delivery, spontaneous abortion, elective termination, stillbirth, small for gestational age

⁵ including clinical manifestations such as lupus nephritis if available

⁶ Maternal interviews: can be up to 4 interviews, depending on gestational age at enroll

ment and include: enrollment interview (any time in pregnancy), interim interview I (20-22 weeks gestations), interim interview II (32-34 weeks gestation), and pregnancy outcome interview (0-6 weeks post-delivery)

⁷ Medical record review will occur at 0-12 months post-delivery for pregnancy information and 1 year post-delivery for infant information

⁸ The ASQ-3 will be sent electronically to the participant or, if the participant prefers, a hard copy questionnaire will be mailed for completion.

⁹ Data also collected from the study dysmorphological examination

8.5. Study size

The proposed sample sizes in each of the study groups are as follows:

- 200 women exposed to belimumab at any time from 3 months prior to the first day of LMP through the end of pregnancy
- 200 women with SLE, unexposed to belimumab

An enrollment of 200 participants in each of the cohort groups is planned over 5 years. Based on previous experience with the MotherToBaby/OTIS Autoimmune Diseases in Pregnancy Project, the expected proportion of women to enroll in first trimester is approximately 70% [Chambers, 2019a]. It is estimated that participants will be an average of 7-10 weeks post-LMP at the time of enrollment. Given this mean gestational timing at enrollment, the anticipated live-birth rate is 85%, which includes a spontaneous abortion and elective abortion rate of 10% [Wilcox, 1988; Zinaman, 1996; Kanmaz, 2019; Chambers, 2019a] and an estimated lost to follow-up rate of 5% [Chambers, 2018], this will result in 170 pregnancies with at least one live born infant in each cohort at the end of recruitment. As a conservative estimate, the power calculations were also conducted assuming a live-birth rate of 80%, which includes a spontaneous abortion and elective abortion rate of 15% [Chambers, 2016], and an estimated lost to follow-up rate of 5%. This conservative estimate will result in 160 pregnancies with at least one live born infant in each cohort at the end of recruitment.

This study is designed to serve as an early warning system to identify a previously unrecognized major teratogen by identifying major birth defects in infants of exposed mothers. For less potent teratogens or for drugs and biological products that cause other adverse pregnancy outcomes, the study can function as a signal detection study and generate hypotheses that can be tested in other studies using other methods that may be better powered to assess these outcomes (FDA, 2019).

Table 4 gives the minimum detectable effect sizes with 80% power [two-sided significance level 0.05]) for the primary outcome of major birth defects. Table 4 includes

varying expected live births in each cohort, using varying rates of SAB/elective terminations and includes varying background rates of major birth defects, based on existing literature on pregnant women with SLE [Vinet, 2012; Gladman, 2010]. As a reference, the effect size has also been calculated based on the general population background rate of major birth defects of 2.8% in the Atlanta metropolitan area [CDC, 2017].

Table 4 Risk estimates for belimumab-exposed pregnancies relative to the primary comparison group for the primary outcome; all estimates use an α -level of 0.05 and power of 0.8 (80%).

Outcome	N in Each Group*	Target Enrolled N in Each Group	Rate in Comparison Group**	Relative Risk***
Using background rates of primary outcome within SLE population				
Major birth defects	160	200	13% ^a	1.9
Major birth defects	160	200	5% ^b	2.8
Major birth defects	170	200	13% ^a	1.9
Major birth defects	170	200	5% ^b	2.7
Using background rates of primary outcome within general population as reference				
Major birth defects	160	200	3% ^c	3.5
Major birth defects	170	200	3% ^c	3.4

N= number of pregnancies with at least one live born infant

*Sample size for the first two rows of the table allows for spontaneous abortion and elective abortion rate of 15% (Chambers, 2016) and lost to follow-up rate of 5%; sample size (Chambers, 2018) for the following two rows of the table allows for spontaneous abortion and elective abortion rate of 10% (Wilcox, 1988; Zinaman, 1996; Kanmaz, 2019; Chambers, 2019a), and lost to follow-up rate of 5%.

**Sample size for major birth defects based on varying prevalence in the SLE comparison group. The 13% is an upper end estimate from Vinet et al, the 5% is a median estimate from Gladman, 2020 and the 3% is the estimate from CDC; sample size based on prevalence within the general population (CDC, 2017). Power calculations performed in open-sourced statistical programming language R software.

*** Minimum relative risk (RR) detectable with 80% power.

^aVinet, 2012; ^bGladman, 2010; ^cCDC, 2017

Group sample sizes of 160 in each group achieve 80% power to detect a ratio of 1.9 to 2.8 when the null-hypothesized ratio is 1.0 and when background rates of major birth defects in pregnant women with SLE are used. The test statistic used is the two-sided Score test [Farrington, 1990]. The significance level of the test was targeted at 0.050. For the secondary outcome of spontaneous abortion, allowing for an elective abortion rate of 5% and a lost to follow-up rate of 5%, an estimated 180 pregnancies are expected in each cohort at the end of recruitment. Group sample sizes of 180 in each group achieve

80% power to detect a ratio of 2.1 when the null hypothesized ratio is 1.0 and when a background rate of spontaneous abortion of 10% is used. The test statistic used is the two-sided Score test [Farrington, 1990]. The significance level of the test was targeted at 0.050.

